### C. Study Design and Research Methods

**Schema:** Single-arm Phase II

surgery for breast cancer (either lumpectomy or mastectomy) with involved regional lymph nodes by axillary dissection or sentinel lymph node biopsy  
 $\pm$  neoadjuvant or adjuvant chemotherapy

adjuvant hypofractionated radiation (4005cGy in 15 fractions over three weeks) to the breast or chest wall **and** the undissected regional lymphatics

Routine follow-up visits will be performed in accordance with routine standard of care practice and as clinically indicated; however visits before radiation (baseline), and at 6, 12, 36, and 60 months will include a protocol mandated history and physical exam to include toxicity grading by the physician as well as quality of life questionnaires by the patient. Patients may see study or other oncologic clinicians in between these intervals for follow-up, though toxicity data collection will not be required at these visits. Mammography for any remaining intact breast should be performed annually or as clinically indicated. All protocol therapy and follow-up visits, are anticipated to be covered by the patient and/or their medical insurance provider.

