## **E. Potential Scientific Problems:**

As with any prospective, single-institution study, sufficient patient accrual is a potential scientific problem that may limit statistical power. Over the last two years, we have treated 142 potentially eligible patients at the University of Colorado Denver. While some eligible patients will undoubtedly decline enrollment, we do expect this study to be particularly attractive to patients given that the proposed treatment is two weeks shorter than standard therapy. It is estimated that this trial will accrue, on average 8 patients per month over all sites, 5 patients per month at the UC Denver campus, and 1-2 patients per month at North and South campuses. Based on our required sample size of 106 patients (justification below), it will take approximately 18-22 months to complete accrual once the study is open at all three campuses.. The primary endpoint will be reported after all patients have been followed for one year.

Accrual.

If accrual is slower than expected and at least 50 patients reach one year of follow-up while total accrual is still fewer than 100 patients, then barriers to accrual will be reconsidered and corrective measures taken. We will also evaluate our event rate at that time to determine whether our 95% confidence interval will satisfactorily exclude the unacceptable event rate of 50% set forth a priori (see sample size justification – Section F.c.), understanding that our limited sample size in this situation may limit statistical power and result in an unacceptably wide confidence interval.

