**F. Data Analysis Plan:**

(a) Definition of primary endpoint: Composite endpoint of six binary outcomes at one year. These are defined below with an estimated composite event rate of 40%. Each event will count equally, and a composite event will be scored only once per patient.

1. lymphedema – an increase in inter limb arm circumference of at least 10% in the lower arm or the upper arm, or both, compared with the contralateral arm at the same time point, will be judged to be clinically significant lymphedema. Arm circumference 15 cm above the medial epicondyle (upper arms) and 15 cm below the medial epicondyle (lower arms) will be measured at 6, 12, 36, and 60 months by clinicians.
2. shoulder stiffness – reported by patient questionnaire [EORTC QLQ-C3014 and breast-cancer module (BR23)].
3. symptomatic rib fracture – diagnosed by evidence of a correlative lesion on plain film or CT.
4. ischemic heart disease – new development of angina with corresponding EKG changes, or myocardial infarction
5. pneumonitis – CTCAE  $\geq$  Grade 2 (requires steroids).
6. brachial plexopathy – CTCAE  $\geq$  Grade 2 (symptomatic, limits ADLs).

(b) Definition of secondary outcomes/endpoints:

1. axillary recurrence – Recurrent disease presentation within axillary lymph node levels I, II, or III. Note that supraclavicular region is not included in this endpoint as in AMAROS historically.

2. local-regional failure free survival – time from date of enrollment to earlier of clinical detection of any ipsilateral recurrent disease to the breast/chest wall or regional lymph nodes (levels I, II, III, supraclavicular, and internal mammary lymph nodes) or death.
3. distant metastasis-free survival – time from date of enrollment to earlier of clinical detection of metastatic disease beyond the breast/chest wall and regional lymph nodes or death.
4. overall survival – time from date of enrollment to date of death from any cause.
5. quality of life [EORTC QLQ-C3014 and breast-cancer module (BR23)].

(c) Analytic plan for primary objective: This analysis will be performed after all patients have been entered and followed for a minimum of one year. All eligible patients (as defined above) that begin protocol treatment will be included in the analysis.

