A non-inferiority margin of 10% was chosen after extensive consultation with multiple radiation oncologists. Note this margin is an absolute difference between the toxicity event rate of standard treatment (assumed to be 40%) and that of proposed treatment, where a higher rate indicates treatment is more toxic. The sample size calculation is based powering the study with 80% power and 5% significance level. The sample size is dependent on the actual absolute difference between the toxicity event rate of standard treatment and that of the proposed treatment. When it is assumed that the actual toxicity event rate of proposed treatment is 2% lower (absolute difference) than that of standard care, a total number of 106 patients accomplishes abovementioned power. If less than 44 patients out of 106 are observed to have adverse event, we will conclude that the proposed treatment is non-inferior to standard treatment. Assuming an estimated drop-out rate of 5% of patients lost to follow-up, the calculated total number of patients will be inflated accordingly to 112.

The initial treatment report will contain the following:

1. study accrual rate;
2. tabulation of all cases entered, and any patients excluded from the analysis with reasons for exclusion;
3. distribution of important prognostic baseline variables;
4. compliance rates of treatment delivery with respect to the protocol prescription;
5. observed results with respect to the primary endpoint described above.

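### Meeting the primary rule shows a composite rate below a fixed 50%; calling that non-inferiority to standard treatment keeps its 5% error limit only if the true standard rate is about 39% or higher

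*Combined protocol and SAP*

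**What the plan says.** Section IV.C describes the design as "Single-arm Phase II", with no standard-treatment arm.

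Section IV.F(a) defines the primary endpoint as a composite of six binary outcomes at one year, scored once per patient, with an "estimated composite event rate of 40" per cent. Section IV.F(c) uses the same figure for the comparator, the "toxicity event rate of standard treatment (assumed to be 40" per cent). Neither place gives a source, a number of patients, a confidence interval or a derivation from the six components.

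On the margin, IV.F(c) states: "A non-inferiority margin of 10% was chosen after extensive consultation with multiple radiation oncologists". It is absolute, so the limit is 40% + 10% = 50%. The accrual paragraph under Potential Scientific Problems names that limit directly, asking whether the interval will "exclude the unacceptable event rate of 50% set forth a priori".

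The sample size is set for "80% power and 5% significance level", supposing the "actual toxicity event rate of proposed treatment is 2% lower (absolute difference) than that of standard care". This gives 106 evaluable patients, raised to 112 for 5% drop-out. Fewer than 44 patients with an event leads to the statement that "we will conclude that the proposed treatment is non-inferior to standard treatment".

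**The concern.** Non-inferiority to standard treatment is a statement about a difference between two rates. This rule uses one observed rate and one fixed number. No standard-treatment patient is measured in the trial, and no uncertainty in the 40% enters the cut-off. The 5% level attaches to the claim that the composite rate is below 50%. It carries over to the non-inferiority claim only as far as the 40% can be relied on.

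If the true standard rate on this composite is lower than assumed, a treatment that exceeds it by the whole margin can pass too often, and the primary report would call it non-inferior. If the true standard rate is higher, a treatment that is no worse than standard may fail.

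**Working it through.** **Inputs from the plan.** Limit p0 = 0.40 + 0.10 = 0.50; design alternative p1 = 0.40 − 0.02 = 0.38; power 80%; significance level 5%, sidedness not stated; N = 106; pass if X ≤ 43 (fewer than 44).

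**Step 1: reproduce N.** One-sample test, one-sided 5%, null and alternative variances:

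n = [1.645·√(0.50·0.50) + 0.842·√(0.38·0.62)]² / (0.50 − 0.38)² = [0.8224 + 0.4085]² / 0.0144 = 105.2, so 106.

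An exact binomial search also gives 106 as the smallest N. Drop-out: 106 / 0.95 = 111.6, so 112. The same formula at two-sided 5% gives 134. A two-arm non-inferiority comparison of 38% with 40%, with a 10-point margin and one-sided 5%, needs about 205 per arm. The plan's figure is therefore that of a one-arm test against 50%.

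**Step 2: error rate of the non-inferiority claim.** Let s be the true standard rate. At the edge of the margin the new treatment has rate s + 0.10, and the false-claim probability is P(X ≤ 43 | 106, s + 0.10), exact binomial. The documents do not bound s, so the values other than 40% are assumed.

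| True standard rate s | Pass if new = s + 10 points (false claim) | Pass if new = s | Pass if new = s − 2 points |
|---|---|---|---|
| 30% | 58.9% | 99.2% | 99.8% |
| 35% | 20.6% | 90.3% | 95.9% |
| 38% | 7.5% | 74.2% | 86.0% |
| 39% | 5.0% | 66.9% | 80.6% |
| 40% | 3.2% | 58.9% | 74.2% |
| 42% | 1.2% | 42.3% | 58.9% |
| 45% | 0.2% | 20.6% | 34.3% |

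**Step 3: where the 5% limit breaks.** P(X ≤ 43 | 106, p) equals 5% at p = 0.490, which is the exact one-sided 95% upper limit for 43/106. Subtracting the margin, the limit holds when s is at least about 0.490 − 0.100 = 39.0%.

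**Step 4: the cut-off against the stated power.** At s = 40%:

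- X ≤ 43 (the written rule): alpha 0.032, power at 38% 0.742.
- X ≤ 44: alpha 0.049, power at 38% 0.801.

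The stated 80% matches 44 or fewer, not fewer than 44. With 44 or fewer, the threshold in Step 3 moves to about 39.96%, and the false-claim probabilities at 38%, 35% and 30% become 10.7%, 26.7% and 66.3%.

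**Step 5: the level to be stated.** At 43/106 the exact one-sided 95% upper limit is 49.0%, but the upper end of the exact two-sided 95% interval is 50.5%. A claim of being below 50% is supported at one-sided 5% and not by a two-sided 95% interval. The accrual paragraph refers only to a 95% confidence interval, so the level has to be named.

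**The case against.** Single-arm phase II trials are routinely judged against a fixed benchmark, and this plan is open about doing so. It says single-arm, calls the 40% assumed and estimated, names 50% as the limit, and in section G presents the trial as groundwork for randomized Phase III trials. A careful reader can see that the claim is conditional. All of that stands, and it is why the design is not in question. But none of those passages qualifies the sentence in IV.F(c) that states the conclusion.

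Four stronger readings are tempting, and the documents do not support them.

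- A reader might infer that the 5% limit holds only if 40% is exactly right. It does not: the dependence runs one way. The limit holds at about 39% and above, and at exactly 40% the written rule gives 3.2%.
- A reader might infer that the 45% row shows harm due wholly to a wrong benchmark. With equal rates the rule passes only 58.9% of the time even at 40%, because the study is powered for a new-treatment rate of 38%. The fall to 20.6% has to be read from that starting point.
- A reader might infer that no historical data lie behind the 40%. The documents only fail to give a source. The follow-up section ties the lymphedema and shoulder definitions to cited trials, so data may have been used.
- A reader might infer that the true standard rate is in fact 30% or 35%. Nothing in the documents says so; those rows show sensitivity only.

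**Conclusion.** The concern holds for the wording of the conclusion. Passing the rule is evidence, at one-sided 5%, that the one-year composite rate is below 50%. It is evidence of non-inferiority to standard treatment at that level only if the true standard rate is about 39% or higher, which leaves roughly one point of slack under an unsourced 40%. At an assumed 38% the false-claim probability already exceeds 5%, and at an assumed 35% it is about four times the limit. Above 40% there is no inflation of false claims, only loss of power.

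These figures assume 106 evaluable patients, independent outcomes, the rule read as 43 or fewer, and a new treatment exactly 10 points worse than standard. The plan should be changed before the primary analysis, because the change alters what the trial may formally conclude.

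**What to change.** 1. Reword the conclusion in IV.F(c): meeting the rule shows, at one-sided 5%, that the one-year composite event rate is below the prespecified unacceptable rate of 50%. Any mention of non-inferiority should be expressly conditional on a standard rate of 40%.
2. Add a small table of pass probabilities over a range of standard rates, labelled as assumed, as in Step 2.
3. State where the 40% comes from and how precise it is, or say that it is a judgement. Component rates alone will not settle it: for a composite scored once per patient, the overlap between components also matters.
4. Do not carry the cut-off over unexamined. Either state 44 or fewer, which matches the planned 80% power (alpha 0.049, power 0.801), or keep fewer than 44 and report its 74.2% power. Build the table for whichever rule is kept.

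The single-arm design and the sample size need not change. The cost is one reworded sentence, one table, the reconciliation of the cut-off and some documentation work on the 40%. The downside is a more modest headline claim.

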#### **G. Summarize Knowledge to be Gained:**

This prospective study will provide valuable information on the safety and tolerability of hypofractionated, short-course radiotherapy after surgery for breast cancer patients. Based on previously published reports in analogous but slightly different scenarios, we hypothesize that hypofractionation will prove to be as good or better than conventionally fractionated radiation that takes 50% (two weeks) longer to administer. However, it is important to document this thoroughly in a prospective manner with informed consent. Detailed information on the safety and efficacy of hypofractionation in the modern era of 3D treatment planning is needed and will prove instructive to design of subsequent randomized, multi-institution Phase III trials. If ultimately proven safe and effective, further transition of national practice care patterns toward a hypofractionated approach would result in substantial societal cost savings with respect to healthcare expenditures and resource utilization.

## Appendix A

Study Calendar	
Visit	Studies performed
Baseline (prior to RT start)	
 
• Consent
 
• History and Physical Exam, including weight and height
 
• Toxicity grading by CTCAE
 
• Lymphedema measurement (bilateral)
 
• Shoulder mobility measurement (goniometer – four excursions)
 
• TSH lab
 
• EORTC QLQ-C30 and BR.23 questionnaire
 

Radiation On-Treat Visit - Week 1	
 
• Toxicity grading by CTCAE
 

Radiation On-Treat Visit - Week 2	
 
• Toxicity grading by CTCAE
 

Radiation On-Treat Visit - Week 3	
 
• Toxicity grading by CTCAE
 

Radiation On-Treat Visit - Week 4 (if applicable)	
 
• Toxicity grading by CTCAE
 

Follow-Up Six-Months (+/- 30 days from RT end)	
 
• History and Physical Exam, including weight
 
• Toxicity grading by CTCAE
 
• Lymphedema measurement (bilateral)
 
• Shoulder mobility measurement (goniometer – four excursions)
 
• EORTC QLQ-C30 and BR.23 questionnaire
 

Follow-Up One-Year (+/- 30 days from RT end)	
 
• History and Physical Exam, including weight
 
• Toxicity grading by CTCAE
 
• Lymphedema measurement (bilateral)
 
• Shoulder mobility measurement (goniometer – four excursions)
 
• TSH lab
 
• EORTC QLQ-C30 and BR.23 questionnaire
 

Follow-Up 36 months (+/- 60 days from RT end)	
 
• History and Physical Exam, including weight
 
• Toxicity grading by CTCAE
 
• Lymphedema measurement (bilateral)
 
• Shoulder mobility measurement (goniometer – four excursions)
 
• TSH lab
 
• EORTC QLQ-C30 and BR.23 questionnaire
 

Follow-Up 60 month (+/- 60 days from RT end)	
 
• History and Physical Exam, including weight
 
• Toxicity grading by CTCAE
 
• Lymphedema measurement (bilateral)
 
• Shoulder mobility measurement (goniometer – four excursions)
 
• TSH lab
 
• EORTC QLQ-C30 and BR.23 questionnaire
 

## Study (Non-SOC) Calendar

15 (+/- 4) treatments

~ August 2015 ~						
Sun	Mon	Tue	Wed	Thu	Fri	Sat
						1
2	3 Radiation (267cGy)	4 Radiation (267cGy)	5 Radiation (267cGy)  On Treat Visit (anytime week 1)	6 Radiation (267cGy)	7 Radiation (267cGy)	8
9	10 Radiation (267cGy)	11 Radiation (267cGy)	12 Radiation (267cGy)  On Treat Visit (anytime week 1)	13 Radiation (267cGy)	14 Radiation (267cGy)	15
16	17 Radiation (267cGy)	18 Radiation (267cGy)	19 Radiation (267cGy)  On Treat Visit (anytime week 1)	20 Radiation (267cGy)	21 Radiation (267cGy)	22
23	24	25	26	27	28	29
30	31	Notes:
